**The Effect of Leukocyte Platelet
Rich Fibrin (L-PRF) Membrane in
The treatment of Localized
Gingival Recession
(Randomized Controlled Clinical
Study)**

Methodology

Date:3/11/2020

Sample selection and assignment:

Twenty patients who were diagnosed with Miller class I and II gingival recession, participated in this prospective clinical trial.

The patients were recruited from the outpatient clinic of Oral Medicine, Periodontology, oral Diagnosis and Radiology Department, Faculty of Dentistry, Ain Shams University. The purpose of the study was explained to all patients and an informed consent was signed before the conduction of the study. The proposal was presented to the faculty of Dentistry Ain Shams University Research Ethics committee and was approved before starting the research with number (453).

Patient selection:

Inclusion Criteria:

- 1- Systemically healthy patients (*American Society of Anesthesiologists I; ASA I*).
- 2- Age range (20 -40) years.
- 3- Good compliance with the plaque control instructions following initial therapy.

Patients: Materials and Methods

- 4- Patients diagnosed with localized gingival recession ***Miller*** class I or II in anterior and premolar teeth (maxillary or mandibular)
- 5- Availability for follow up and maintenance program.

Exclusion criteria:

1. Patient suffering from periodontitis
2. Presence of smoking habit.
3. Presence of occlusal interferences.
4. Pregnant and lactating females.
5. Vulnerable group of patients (handicapped, mentally retarded and prisoners) (according to the recommendation of esthetical committee of Faculty of Dentistry Ain Shams University).
6. Carious teeth and teeth with periapical infection.

Calculation of Power analysis:

The study consisted of two groups; **group (I) and group (II)** each group included 10 patients. The number of patients in each group was determined by sample size calculation based upon the results of *Tunali et al. (2015)*. Using alpha level of 0.05 (5%) and β level of 0.20 (20%) i.e. power = 80%; the estimated minimum required sample size was approximately 4 cases in each group. Patients were randomly selected using computer generated randomization (www.randomizer.org). Allocation concealment was achieved using a sealed coded opaque envelope containing treatment of the subject.

Grouping Criteria:

Group I: (L-PRF+ coronally repositioned flap):

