Included 10 patients who received L-PRF membrane with coronally repositioned flap for the treatment of gingival recession

Group II: (Sub epithelial connective tissue+ coronally repositioned flap):

Included 10 patients who received sub-epithelial connective tissue graft with coronally repositioned flap for the treatment of gingival recession

III- Clinical parameters Assessments:

For the selected sites, the following clinical parameters were assessed using periodontal probe (UNC-15) * preoperative (baseline), 3, 6 and 9 months after the surgical procedure.

1. Plaque index (*Silness and Löe 1964*).
2. Gingival Index (*Löe and Silness 1963*).
3. Probing depth (PD) (*Glavind and Loe, 1967*).
4. Clinical attachment level (CAL) (*Glavind and Loe 1967*).
5. Gingival recession depth.
6. Keratinized tissue width.

* UNC15 Single-ended, color-coded probe. ergonomic handle. University of North Carolina, Hu Friedy, USA.

Patients: Materials and Methods

- **Pre surgical therapy:**

- Full Conventional periodontal treatment including supra, sub-gingival scaling and root planning were performed using ultra sonic[†] and hand scalers[‡] and hand curettes[§].
- Oral hygiene instructions (regular brushing 2 times/day and flossing) were repeated until patients had achieved a proper level of oral hygiene where plaque index (PI) and gingival index (GI) ≤ 1 .

[†] Woodpecker UDS-K LED Ultrasonic Scaler EMS Compatible, Faye dental professional supplies, China

[‡] Sickle scaler, posterior jacquette, Hu-Friedy ,USA

[§] Universal Curettes(2R/2L),(4R/4L), Hu-Friedy ,USA

IV-Surgical protocol:

Group (I)

- 1) Anesthesia (Articaine HCL 4% containing epinephrine at a concentration of 1:100,000)** was administrated at the recession area.
- 2) An intrasulcular incision was made with a surgical blade (15c)^{††} on the buccal aspect of the involved tooth. The incision was extended horizontally to dissect the facial aspect of the adjacent papillae both mesially and distally.
- 3) Two oblique releasing incisions were made mesial and distal to the horizontal incision beyond the mucogingival junction.
- 4) A full-thickness flap was raised with a periosteal elevator up to the mucogingival junction. A partial-thickness dissection was done apically, leaving the underlying periosteum in place.
- 5) A mesio-distal and apical dissection parallel to the vestibular lining mucosa was performed to release residual muscle tension and facilitate the passive

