The patients were recalled every month for examination of the surgical area and for plaque removal when necessary

- Clinical and esthetic parameters were evaluated and scored by a separate blinded operator at 3, 6 and 9 months postoperative.

Esthetic outcome evaluation was done using Root coverage esthetic score (RES) system (Cairo et al. 2009)
the RES include the following parameters

- Level of the gingival margin (**GM**): Zero points = failure of root coverage (gingival margin apical or equal to the baseline recession); 3 points = partial root coverage; 6 points = complete root coverage (**CRC**).
- Marginal tissue contour (**MTC**): Zero points = irregular gingival margin (does not follow the CEJ); 1 point = proper marginal contour/ scalloped gingival margin (follows the CEJ).
- Soft tissue texture: Zero points = scar formation and/or keloid like appearance; 1 point = absence of scar or keloid formation.

Patients: Materials and Methods

- Mucogingival junctional alignment (**MGJ**): Zero points = MGJ not aligned with the MGJ of adjacent teeth; 1 point = MGJ aligned with the MGJ of adjacent teeth.
- Gingival color (**GC**): Zero points = color of tissue varies from gingival color at adjacent teeth; 1 point = color of the tissue is similar to the gingival color of the adjacent teeth

These parameter were measured 3, 6 and 9 post-surgical

Volumetric assessment after 9 months :

Impressions were done using addition silicon impression^{\$\$\$\$\$} material at baseline and 9 months.

These impressions were poured using extra hard stone ***** material. All the stone cast models were digitized using optical scanner. The digital surface models were imported as STL files into the software for volumetric analysis (plastycad, 3diemme, Como, Italy). On each cast 4 fixed points were determined and remained untouched during the observation time. These 4 fixed points defining a

\$\$\$\$\$ Elite HD+ Putty Soft addition silicon Manufacturer Part No: ZHC203000. Zhermack SpA, Italy

*****Rock extra hard stone, Manufacturer Part No: C410339, Zhermack SpA, Italy

Patients: Materials and Methods

base plane for one series of measurements. The relevant area for the measurements of volume changes was defined by the mesial and distal surfaces of adjacent teeth.

[figure not shown]
[figure not shown]

Fig (2): Four fixed points defining a base plane for one series of measurements

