The digital images obtained were transferred into digital imaging software, which was used to superimpose and match the images obtained in one coordinate system. For superimposition of different images, the buccal surfaces of the adjacent teeth were used as a reference. The scanned cast images were superimposed and subtracted and the soft tissue volume was determined for any volume changes

Patients: Materials and Methods

To evaluate the differences in form between the preoperative and postoperative casts, the variation between images was calculated by subtracting the corresponding phase images, leaving a phase difference image.

Fig(3): Diagram showing the superimposition for the volumetric assessment of the soft tissue thickness

- All data were collected and statistical analysis was done.

VI-Statistical analysis:

Categorical data were presented as frequencies and percentages and were analyzed using chi square test. Numerical data were tested for normality using Shapiro-Wilk test and were presented as mean and standard deviation values. Parametric data were analyzed using one-way ANOVA followed by Tukey's post hoc test for intergroup comparisons and one-way repeated measures ANOVA followed by Bonferroni post hoc test for intragroup comparisons. Non-parametric data were analyzed using Kruskal-wallis test followed by pairwise comparisons utilizing Mann Whitney U test with Bonferroni correction for intergroup comparisons and Friedman's test of repeated measures followed by multiple pairwise comparisons utilizing Wilcoxon signed-rank test with Bonferroni correction for intragroup comparisons. The significance level was set at $p \leq 0.05$ within all tests. Statistical analysis was performed with IBM SPSS Statistics Version 26 for Windows

††††† IBM Corporation, NY, USA.

‡‡‡‡‡ Statistical Package for Social Science, Inc., an IBM Company.

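### For the clinical parameters read at four visits, single-step Bonferroni over six within-arm pairs is more conservative than needed with 10 patients per arm

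*Protocol*

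**What the plan says.** The section VI-Statistical analysis gives two within-arm rules. Parametric data get "one-way repeated measures ANOVA followed by Bonferroni post hoc test for intragroup comparisons". Non-parametric data get Friedman's test, "followed by multiple pairwise comparisons utilizing Wilcoxon signed-rank test with Bonferroni correction for intragroup comparisons". The threshold is common to all: "The significance level was set at $p \leq 0.05$ within all tests".

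The number of pairs follows from the visit schedule. The six clinical parameters (plaque index, gingival index, probing depth, attachment level, recession depth, keratinized tissue width) are assessed "preoperative (baseline), 3, 6 and 9 months after the surgical procedure", which is four visits. For the root coverage esthetic score (RES) the protocol says "These parameter were measured 3, 6 and 9 post-surgical", which is three visits. Impressions for the volumetric outcome are taken with silicone "material at baseline and 9 months", which is two visits. On size, "each group included 10 patients".

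The protocol does not state the Bonferroni factor, the list of pairs, whether the Wilcoxon p-value is exact or asymptotic, or whether the pairwise tests depend on a significant omnibus test.

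**The concern.** Signed-rank p-values are discrete, and patients with a zero difference drop out of the usual test. With 10 patients and a multiplier of 6, a few unchanged readings can put 0.05 out of reach for a pair of visits, however consistent the remaining changes are.

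Unchanged readings are plausible here. Plaque and gingival indices are ordinal scores, and both must be at or below 1 before surgery, so they have little room to move. Depths are read with a manual probe. Such data are also likely to fail the Shapiro-Wilk test and so enter the non-parametric branch.

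What is at stake is the power to show change from baseline within an arm.

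**Working it through.** **Inputs.** From the protocol: 10 patients per arm, four visits for clinical parameters, level 0.05. Assumed: two-sided tests and all pairs compared. The protocol gives no figure for within-arm power. Its only computed figure, about 4 patients per group, cannot be reproduced because no effect size or SD is given, and it is not used here.

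**Number of pairs.** Four visits: 4 × 3 / 2 = 6. RES, three visits: 3. Volume, two visits: 1.

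**Smallest attainable Wilcoxon p.** Let m be the number of patients with a non-zero difference, all in the same direction.
- Exact, two-sided: p = 2/2^m.
- Asymptotic, untied: z = [m(m+1)/4] / √[m(m+1)(2m+1)/24].
- Asymptotic, all changes of equal size: z = √m.

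| m | Unchanged | Exact p | Exact × 6 | Exact × 3 | Asymptotic untied × 6 | Asymptotic all equal × 6 |
|---|---|---|---|---|---|---|
| 10 | 0 | 0.0020 | 0.0117 | 0.0059 | 0.0304 | 0.0094 |
| 9 | 1 | 0.0039 | 0.0234 | 0.0117 | 0.0461 | 0.0162 |
| 8 | 2 | 0.0078 | 0.0469 | 0.0234 | 0.0703 | 0.0281 |
| 7 | 3 | 0.0156 | 0.0938 | 0.0469 | 0.1078 | 0.0489 |
| 6 | 4 | 0.0313 | 0.1875 | 0.0938 | 0.1663 | 0.0858 |

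With the exact test and factor 6, three unchanged patients put that pair out of reach. With two unchanged, all eight changes must go the same way. The asymptotic test can fail already at two unchanged (0.070, untied) or still pass at three (0.049, seven equal changes). Six changes of one unit and one of two units give 0.0114 × 6 = 0.068.

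**A strong omnibus result can coexist with this.** Take seven patients at 3, 1, 1, 1 and three at 2, 2, 2, 2. Friedman's chi-square is 21.0, p = 0.0001. Each baseline contrast has m = 7, so its exact p × 6 is 0.094, and the follow-up pairs show no change. No pair passes. With multiplier 3 all three baseline contrasts pass at 0.047.

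**Why 3 is enough once equality of all four visits is rejected.** Group the visits by equality. The number of true pairwise nulls is 6 (all equal), 3 (three equal), 2 (two pairs), 1 (one pair) or 0. Rejecting overall equality excludes 6, which leaves at most 3. Shaffer's ordered multipliers are then 3, 3, 3, 3, 2, 1. Without the omnibus condition they are 6, 3, 3, 3, 2, 1. For three visits the possible counts are 3, 1 or 0, giving 1, 1, 1 with the condition and 3, 1, 1 without it.

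**Size of the loss, by simulation under assumed values** (baseline 2 to 5 mm, mean change 1.0 mm, SD about 0.7 mm, 10 patients, exact Wilcoxon after Friedman):
- Readings to 1 mm: three or more patients unchanged in 43% to 44% of trials. Baseline versus 9 months succeeds in 42% to 46% with factor 6, and in 63% to 66% with factor 3 or the step-down.
- Readings to 0.5 mm: 63% to 64% with factor 6, 79% with factor 3.
- Friedman significant but no pair significant, factor 6: 16%, 24% and 32% at 1 mm for correlations of 0, 0.5 and 0.8 between follow-up changes; 4%, 8% and 13% at 0.5 mm.
- Family-wise error: at most about 1.3% with factor 6 and 2.6% with factor 3. For the step-down it was at most about 4% in every null setting tried, including one that breaks exchangeability.
- ANOVA branch, unrounded data, paired t: about 81% with factor 6 and 90% with factor 3.

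**The case against.** Bonferroni is valid and standard. It inflates no error, contradicts nothing in the protocol, and touches only within-arm tests, which do not compare the treatments. The pair list, the factor and the form of the p-value may be settled in a statistical analysis plan that is not at hand. All of this stands, so the point is an improvement and not the correction of an error. It remains a point because single-step Bonferroni is a method the protocol does state. The step-down without an omnibus condition rejects everything Bonferroni rejects, and can reject more, at the same family-wise level.

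Several stronger readings are tempting, and the protocol does not support them:
- *The plan requires a significant omnibus test first.* This is a usual reading, but the wording gives only the order of the tests. Without that condition, 6 is the ordinary single-step factor for six comparisons.
- *No result can be significant with three unchanged patients.* The limit binds only the pair of visits that has three zero differences, and only with an exact test, which the protocol does not name.
- *The plan will often show change over visits with no pair differing.* In the simulations this is a minority of trials and depends strongly on rounding and correlation.
- *All outcomes carry the factor of 6.* RES has three pairs, and 0.0156 × 3 = 0.047 is reachable with three unchanged. Volume has one pair.

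A technical objection also has some force. The count of true nulls is derived for equality across visits, and the Friedman and Wilcoxon nulls are not identical. For that branch, error control after the omnibus condition is supported by simulation here and not proved.

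**Conclusion.** The point holds for the six clinical parameters at four visits. Single-step Bonferroni over six pairs is more conservative than 5% family-wise control needs. In the non-parametric branch it can make a pair with three unchanged patients untestable (0.094 at best, if the test is exact). Under the assumed change, SD, 1 mm readings and correlation of 0.5, the cost is about 20 percentage points for baseline versus 9 months (about 45% against about 65%). With 0.5 mm readings it is about 15 points.

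The mean change, SD, rounding and correlation are assumptions, since the protocol gives none of them. The arithmetic limit rests only on a two-sided exact test and all six pairs being compared. The loss is of power alone and matters most for outcomes with many zero differences.

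**What to change.** In VI-Statistical analysis, for outcomes measured at four visits, replace Bonferroni in both intragroup rules by Shaffer's step-down on the six pairwise p-values, with exact p-values for Wilcoxon. State whether pairwise tests are done only after a significant omnibus test.
- If so: ordered multipliers 3, 3, 3, 3, 2, 1, with the ANOVA omnibus decision taken from a sphericity-corrected p.
- If not: 6, 3, 3, 3, 2, 1. This gains less, because some pair must first pass at factor 6. In the worked example above it would rescue nothing.
- RES, three visits: 1, 1, 1 after a significant omnibus test, or 3, 1, 1 without that condition.
- Volume: a single comparison, no correction.

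The cost is wording only: all six contrasts stay and no patient is added. There are two downsides. The multipliers must be applied by hand to unadjusted p-values, outside the SPSS Bonferroni option. An explicit omnibus condition also removes any pairwise claim when the omnibus test is not significant.

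### No primary outcome or decisive visit is named: eight unranked outcomes share one 0.05 rule, and the named corrections do not act across outcomes, nor across visits for the between-group comparisons

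*Protocol*

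**What the plan says.** Protocol, III- Clinical parameters Assessments, gives one unranked list of six measures: plaque index, gingival index, probing depth, clinical attachment level, recession depth and keratinized tissue width. It states that "the following clinical parameters were assessed using periodontal probe (UNC-15) * preoperative (baseline), 3, 6 and 9 months after the surgical procedure".

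VI-Postoperative evaluation and assessment adds the root coverage esthetic score (RES) at 3, 6 and 9 months and a volume change from baseline to 9 months. It says "Clinical and esthetic parameters were evaluated and scored by a separate blinded operator at 3, 6 and 9 months postoperative". That makes eight outcomes. None is called primary, and none of the three post-operative visits is called decisive.

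Calculation of Power analysis states "The study consisted of two groups", with 10 patients each. It continues "The number of patients in each group was determined by sample size calculation based upon the results of" an earlier published study. With alpha 0.05 and 80% power, "the estimated minimum required sample size was approximately 4 cases in each group". No outcome, difference or standard deviation is given.

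VI-Statistical analysis fixes "The significance level was set at $p \leq 0.05$ within all tests". Between groups it names Tukey's post hoc test after one-way ANOVA, or Bonferroni-corrected Mann-Whitney tests after Kruskal-Wallis. Within groups it names Bonferroni-corrected pairwise comparisons after repeated measures ANOVA or Friedman's test.

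**The concern.** A two-arm trial needs one comparison, named in advance, that answers its question. Here the outcome list, the visit schedule, the sample-size paragraph and the analysis section each leave it open. A result at 0.05 on any of eight outcomes counts as significant by the stated rule, and nothing tells the reader how to weigh it against the other seven.

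The analysis section can also reassure wrongly. It names Tukey and Bonferroni, so multiplicity looks controlled. For the comparison of L-PRF with connective tissue graft, these steps adjust nothing.

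**Working it through.** **1. The plan's own figure.** The minimum of about 4 per group cannot be reproduced, because no effect size is given. Solving backwards with the normal formula, d = (z for two-sided 0.05 + z for 80% power) × √(2/n) = (1.960 + 0.842) × √(2/4) = 1.98 standard deviations. The t-test version gives 2.38 two-sided and 2.00 one-sided. This shows how large the assumed effect must have been, but not the outcome it belongs to. The sample size therefore does not identify a primary comparison.

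**2. What the named corrections do.**
- Between groups: two groups give C(2,2) = 1 pair. Tukey's critical value for two groups on 18 degrees of freedom, divided by √2, is 2.101, and the two-sided t critical value is also 2.101. The p-values are the same. A Bonferroni correction over one pair multiplies by 1.
- Within groups: four time points give C(4,2) = 6 visit pairs and three give C(3,2) = 3. Bonferroni over these pairs is a real correction across visits, but it stays inside one arm and one outcome.

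No named step covers several outcomes, or several visits when the arms are compared.

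**3. Size of the effect.** Inputs from the protocol: 10 per arm, 0.05 per test, and eight outcomes, or six if plaque and gingival index are read as hygiene monitoring (Pre surgical therapy uses both as the standard to be reached before surgery). Assumptions: no true difference, two-sided tests, one between-group test per outcome, continuous data, and one common correlation between all tests.

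If tests were independent, the chance of at least one false result would be 1 − 0.95^8 = 33.7% for eight and 1 − 0.95^6 = 26.5% for six. Independence is unrealistic. The same 20 patients supply every measure, and RES overlaps with recession depth: its gingival-margin item ("3 points = partial root coverage; 6 points = complete root coverage") carries 6 of the 10 points (6 + 1 + 1 + 1 + 1). Simulation with correlated tests gives:

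| Common correlation | 0.3 | 0.5 | 0.7 | 0.8 | 0.9 |
|---|---|---|---|---|---|
| 8 outcomes, t-test | 30.5% | 25.8% | 19.8% | 16.1% | 12.4% |
| 6 outcomes, t-test | 24.3% | 21.3% | 17.0% | 14.4% | 11.3% |
| 8 outcomes, exact Mann-Whitney | 26.6% | 23.5% | 18.1% | 15.6% | 12.1% |
| 6 outcomes, exact Mann-Whitney | 21.8% | 19.5% | 15.9% | 13.6% | 10.5% |

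There were 100,000 runs for the t-test and 40,000 for Mann-Whitney (exact size 4.33%, rejecting at U ≤ 23). The Monte Carlo standard error is at most 0.25 percentage points.

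**4. Why one primary outcome rather than a wider correction.** With 10 per arm and 80% power, a two-sided t-test at 0.05 detects 1.32 standard deviations. Bonferroni over eight outcomes (0.05/8 = 0.00625) raises this to 1.79.

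**The case against.** **The statistical analysis plan may hold the detail.** It is not shown, and handling of secondary multiplicity, or whether arms are compared once or at each visit, can properly sit there. That stands, so neither is held against the protocol. The primary outcome is different: it is part of the design, and the sample size depends on it. The protocol also does fix one level for every test and names its corrections.

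**The protocol sets a per-test level, not a success rule.** A reader might infer that one significant outcome is meant to establish a treatment. The text does not say so. The percentages above describe the chance of at least one false result, not the error rate of a stated decision rule. What remains is that no comparison is designated to decide.

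**Visits.** A reader might infer that no correction acts across visits at all, but the within-group Bonferroni does. A reader might also count seven outcomes at three visits plus volume, 7 × 3 + 1 = 22 between-group tests, and quote 1 − 0.95^22 = 67.6%. That assumes visit-by-visit testing, which the text does not state, and independence. Neither is supported.

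**Tied scales.** RES is coarse, and plaque and gingival index must be low before surgery. With 10 per arm, a tie-corrected Mann-Whitney test had size 4.7% on five equally likely levels, 4.1% on an even binary scale and 2.0% on an 85/15 one. These distributions are assumed. The objection stands in direction: the table leans somewhat high. Even if plaque and gingival index contributed nothing, the six-outcome rows would remain.

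**Past tense.** The text reports data collection and analysis as done. A reader might infer that outcomes were chosen after the results were seen. The protocol does not settle this, so the fix covers both cases.

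**Conclusion.** The point holds. The protocol designates no outcome and no visit to decide between the two treatments, and its named corrections do not act across outcomes, nor across visits for the between-group comparisons. This should be fixed.

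With one t-test per outcome and no true difference, the chance of at least one false between-group result is about 12 to 30% for eight outcomes and 11 to 24% for six, against a nominal 5%. The range reflects assumed common correlations of 0.9 to 0.3. These are not in the documents, so the range is illustrative and its ends are not bounds. The missing primary comparison does not depend on these figures.

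**What to change.** Name one primary outcome at one visit. It should be the outcome on which the sample size was based, and the power paragraph should say which that was. If there was none, choose one before outcome data are seen, for example the between-group difference in recession depth at 9 months. That is the last visit, and the only post-operative one at which all eight outcomes are measured.

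Test it at two-sided 0.05. Replace the sentence that sets one level for every test, so that all other outcomes and visits are secondary and are reported as differences with 95% confidence intervals and no confirmatory claim.

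If outcome data have already been seen, label the choice post hoc and all results exploratory. A primary outcome picked at that point does not restore a 5% error rate.

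Cost: if data are unseen, this is a change of wording only, and secondary outcomes can no longer be claimed as proof at 0.05. If data have been seen, no confirmatory claim is possible.
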